# APPENDIX B THE WORLD HEALTH ORGANIZATION (WHO) CLASSIFICATION OF ACUTE MYELOID LEUKEMIA (AML)

### Table 18: WHO classification of AML

AML with recurrent genetic abnormalities
AML with t(8;21)(q22;q22.1);RUNX1-RUNX1T1
AML with inv(16)(p13.1q22) or t(16;16)(p13.1;q22);CBFB-MYH11
APL with PML-RARA
AML with t(9;11)(p21.3;q23.3);MLLT3-KMT2A
AML with t(6;9)(p23;q34.1);DEK-NUP214
AML with inv(3)(q21.3q26.2) or t(3;3)(q21.3;q26.2); GATA2, MECOM
AML (megakaryoblastic) with t(1;22)(p13.3;q13.3);RBM15-MKL1
Provisional entity: AML with BCR-ABL1
AML with mutated NPM1
AML with biallelic mutations of CEBPA
Provisional entity: AML with mutated RUNX1
AML with myelodysplasia-related changes
Therapy-related myeloid neoplasms
AML, NOS
AML with minimal differentiation
AML without maturation
AML with maturation
Acute myelomonocytic leukemia
Acute monoblastic/monocytic leukemia
Pure erythroid leukemia
Acute megakaryoblastic leukemia
Acute basophilic leukemia
Acute panmyelosis with myelofibrosis
Myeloid sarcoma
Myeloid proliferations related to Down Syndrome
Transient abnormal myelopoiesis (TAM)
Myeloid leukemia associated with Down Syndrome
Abbraviations: AMI - aguta myaloganous laukamia: NOS - not otherwise specified: TAM - transient abnormal

Abbreviations: AML = acute myelogenous leukemia; NOS = not otherwise specified; TAM = transient abnormal myelopoiesis.

Source: Arber, 2016.

## APPENDIX C RESPONSE CRITERIA FOR ACUTE MYELOID LEUKEMIA (AML)

The revised recommendations of the European Leukemia Net (ELN) for diagnosis, standardization of response criteria, treatment outcomes, and reporting standards for therapeutic trials in acute myeloid leukemia modified for this protocol.

Table 19: Hematologic/Molecular Response According to ELN Criteria for AML

Response Criterion	Time of Assessment	Absolute Neutrophils (µL)	Platelets (μL)	BM Blasts (%)	Other
Early Treatment assessment	7-10 days after therapy	NA	NA	< 5	
Morphologic Leukemia-free State (MLFS)	Varies by protocol	NA	NA	< 5	Flow cytometry EMD-
Morphologic CR	Varies by protocol	≥ 1,000	≥100,000	< 5	Transfusion EMD-
CR without minimal residual disease (CR MRD -)	Varies by protocol	≥ 1,000	≥100,000	< 5	Molecular/genetic marker - negative, EMD-
Morphologic CR with incomplete blood recovery (CRi)	Varies by protocol	Fulfill all criteria for CR except for residual neutropenia (< $1,000/\mu L$ ) or thrombocytopenia (< $100,000/\mu L$ ).			
Morphologic CR with partial hematologic recovery (CRh)	Per protocol	>500	>50,000	< 5	Absence of peripheral leukemic blasts, EMD-
Partial Remission (PR)	Varies by protocol	≥ 1,000	≥100,000	Decrease ≥ 50 resulting in 5 to 25	Blasts ≤ 5% if Auer rod positive
Hematologic Response (HR)	Varies by protocol	≥ 500 Improvement in hematologic parameters that do not meet criteria for PR, ie, transfusion independence*.			
Stable Disease	Varies by protocol	Absence of CR MRD -, CR, CRi, CRh, PR, MLFS; and criteria for PD not met			
Hematologic relapse after CR MRD -, CR, CRi, CRh	Varies by protocol	Reappearance of leukemic blasts in the peripheral blood or $\geq$ 5% blasts in the bone marrow not attributable to any other cause (eg, bone marrow regeneration after consolidation therapy) or EMD+.			
Molecular relapse after CR MRD	Varies by protocol	Reoccurrence of MRD as assessed by RT-qPCR or by MFC			

Abbreviations: AML = acute myeloid leukemia; BM = bone marrow; CR = complete remission; CRh = morphologic CR with partial hematologic recovery; CRi = morphologic CR with incomplete blood recovery; CRMRD. = CR without minimal residual disease; ELN = European Leukemia Net; EMD = extramedullary disease; EMD- = extramedullary disease negative; EMD+ = extramedullary disease positive; HR = hematologic response; MFC = multiparameter flow cytometry; MLFS = morphologic leukemia-free state; MRD = minimal residual disease; NA = not applicable; PD = progressive disease; PR = partial remission; RT-qPCR = quantitative reverse transcription polymerase chain reaction.

Source: Bloomfield, 2018; Dohner, 2017.

\* Transfusion independence for hematologic response is defined as the absence of any red blood cell or platelet transfusion during any consecutive during the treatment period (Silverman, 2009). Packed red cell and platelet transfusion history for up to beginning study treatment will be collected.

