6.4 Efficacy Assessment
Blood and Bone Marrow Aspirate and/or Biopsy
Bone marrow (BM) aspiration and/or biopsy for disease burden assessments will be collected to
be evaluated for at Screening, end
In addition, bone marrow
aspirates (BMA) or biopsies (BMB) are performed to confirm complete remission (CR) or
morphologic CR with incomplete hematologic recovery (CRi) or morphologic CR with partial
hematologic recovery (CRh), relapse after CR, CRi, or CRh (as assessed by the Investigator based
on CBC with WBC differential results), or disease progression. Additional aspirates and/or
biopsies will be collected as clinically indicated, based on Investigator's medical judgement. Both
bone marrow aspirate and biopsy samples are mandatory at Screening
thereafter, a bone marrow aspirate alone is sufficient, but a biopsy must be collected if the aspirate
is not available and may be collected in addition to the aspirate per institutional practice.

Response to treatment will be assessed by Investigator using local laboratory results according to modified 2017 European Leukemia Network (ELN) AML Response Criteria (Döhner, 2017) for AML and modified IWG Response Criteria (Cheson, 2006) for MDS based on reported hematology laboratory parameters, peripheral blood smear, bone marrow aspirates and/or biopsies. Hematologic response/transfusion dependence will also be evaluated. In addition, CR with partial hematologic recovery (CRh) will be reported for both AML and MDS (Bloomfield, 2018).

AML response criteria will be summarized by best overall response categories: complete remission rate (CRR) defined as CR + CRi + CRh, and objective response rate (ORR, all responses of CR [ie, CRMRD-, morphologic CR, CRh, CRi] + morphologic leukemia free state [MLFS] + partial remission [PR]). For MDS, the CRR is defined as CR, ORR includes all responses (CR + CRh + marrow CR + PR). The efficacy variable of focus will be CRR and ORR. Other measures of clinical activity include duration of remission, duration of response, stable disease rate (MDS only), relapse-free survival, event-free survival, progression-free survival, time to remission/response, transfusion independence, time to AML transformation for MDS subjects, and overall survival (OS) rates at 6 and 12 months.

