#### Progressive disease for AML will be defined as:

- A > 50% increase in bone marrow blast count percentage from the baseline (screening) bone marrow blast count (a minimum 15% point increase is required in cases with <30% blasts at baseline; or persistent bone marrow blast count > 70%, over at least 3 months; without at least a 100% improvement in ANC to an absolute level (> 0.5 x 10^9/L) and/or platelet count > 50 x 10^9/L non-transfused), or
- A > 50% increase in peripheral blasts (WBC × % blasts) to > 25 x  $10^9/L$  (> 25,000/ $\mu$ L) (in the absence of differentiation syndrome), or
- New extramedullary disease.

The date of progressive disease is defined as the first date that there was either a > 50% increase in BM blast count from baseline, a persistence of BM blasts > 70% in subjects with a baseline BM blast count of > 70%, or a doubling of the peripheral blood (PB) blast count.

Treatment failure will be defined as progressive disease or not achieving at least partial remission (PR) by the end of the treatment period. Subjects may continue treatment if they are deriving benefit from treatment without unacceptable toxicity (any CR, MLFS, PR, or SD with demonstrated clinical benefit eg, reduction in transfusion burden), as judged by the Investigator, or until disease progression, loss of clinical benefit, unacceptable toxicity, or decision to withdraw by subject or Investigator. Failure to achieve a response while simultaneously not meeting the criteria for progressive disease will be considered stable disease.

Subjects who discontinue study treatment for reasons other than disease progression (or relapse) or start of a new anticancer therapy will have disease assessments according to the specified

assessment schedule (refer to Section 6.3.2) until progression (or relapse) and/or initiation of new anticancer therapies. For subjects who have discontinued study treatment due to relapse or progression or start of a new anticancer therapy, follow up can be performed by site visits or phone calls. Subjects will be followed they have died, are lost to follow up, withdraw consent for further data collection, or until study closure.

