### 7.2.1.2 Azacitidine

Azacitidine at 75 mg/m^2 is administered on Days 1-7 (or Days 1-5 and 8-9) of each 28-day cycle as an IV or SC injection per local prescribing information and institutional standard of care.

BSA for subject dosing should be calculated on the first day of each dosing cycle. BSA should be calculated per institutional standard, however, the Dubois formula

is preferred. If a subject's body weight changes by more than 10% compared with baseline body weight, or compared with a previous body weight value that required a dose adjustment, then the dose of azacitidine should be recalculated. The dose during a treatment cycle should not be amended.

Subjects may receive best supportive care as needed (please refer to local prescribing information and local therapeutic guidelines for more details on available formulations, preparation, storage conditions [eg, refrigeration], the approved indications, known precautions, warnings, and adverse reactions of best supportive care; see current version of Prescribing Information), including antibiotics and transfusions, per Investigator's discretion.

7.2.1.3	Venetoclax		

On Day 1 of each cycle, CC-95251, azacitidine, and venetoclax will be administered and subjects should be observed for between infusions. will be taken orally hours

Each dose should be taken with a meal and water and consumed over as short of a time as possible. Subjects should be instructed to swallow tablets whole and to not chew or crush the tablets.

Subjects will be given a medication diary to record the time of venetoclax administration for athome administration. All efforts should be made to administer venetoclax on all scheduled days of each 28-day treatment cycle.

[figure not shown]
Any

missed doses should be documented in the subject's medication diary and not be taken beyond the last scheduled day of venetoclax administration.

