## APPENDIX E RESPONSE CRITERIA FOR MYELODYSPLASTIC SYNDROMES (MDS)

The revised recommendations of the International Working Group (IWG) for diagnosis, standardization of response criteria, treatment outcomes, and reporting standards for therapeutic trials in myelodysplastic syndromes (MDS) modified for this protocol.

Table 21: Modified IWG Response Criteria for MDS

Category	Response criteria (responses must last at least 4 weeks)			
Complete remission (CR)	Bone marrow: $\leq$ 5% myeloblasts with normal maturation of all cell lines a Persistent dysplasia will be noted a,b Peripheral blood c - Hemoglobin $\geq$ 11 g/dL  - Platelets $\geq$ 100 $\times$ 10  /L  - Neutrophils $\geq$ 1.0 $\times$ 10  /L b - Blasts 0%			
Morphologic CR with partial hematologic recovery (CRh)	Bone marrow: $\leq 5\%$ myeloblasts with normal maturation of all cell lines a Persistent dysplasia will be noted a,b Peripheral blood c - Hemoglobin $\geq 11$ g/dL  - Platelets $> 50 \times 10^9$ /L  - Neutrophils $> 0.5 \times 10^9$ /L b - Blasts $0\%$			
Partial remission (PR)	All CR criteria if abnormal before treatment, except:  Bone marrow blasts decreased by $\geq 50\%$ over pretreatment but still $> 5\%$ Cellularity and morphology not relevant			
Marrow CR b ± Hematologic Improvement (HI)	Bone marrow: ≤ 5% myeloblasts and decrease by ≥ 50% over pretreatment b Note: Blasts at baseline must be ≥ 5% in order for subject to be evaluable for Marrow CR d Peripheral blood: if HI responses, they will be noted in addition to marrow CR b			
Stable disease (SD)	Failure to achieve at least PR, but no evidence of progression for >			
Failure	Death during treatment or disease progression characterized by worsening of cytopenias, increase in percentage of bone marrow blasts, or progression to a more advanced MDS FAB subtype than pretreatment			
Relapse after CR or PR	At least 1 of the following:			
	
 
Return to pretreatment bone marrow blast percentage
 
Decrement of ≥50% from maximum remission/response levels in granulocytes or platelets
 
Reduction of Hgb concentration by ≥ 1.5 g/dL or transfusion dependence
 
			
Cytogenetic Response	Complete – Disappearance of the chromosomal abnormality without appearance of new ones  Partial – At least 50% reduction of the chromosomal abnormality			

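### The AML CRh row in Table 19 lacks the transfusion condition that CR appears to carry and CRi inherits, so a transfused platelet count can enter AML CRR; the MDS CR row in Table 21 has a related, partly guarded gap

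*Combined protocol and SAP*

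**What the plan says.** **AML, Appendix C, Table 19.**
- Morphologic CR needs ANC of at least 1,000, platelets of at least 100,000 and marrow blasts below 5%. Its last column reads "Transfusion EMD" negative, with the operator after the transfusion entry not visible.
- CRi is defined by reference to CR: "Fulfill all criteria for CR except for residual neutropenia" (below 1,000) or thrombocytopenia (below 100,000).
- CRh needs ANC above 500, platelets above 50,000, marrow blasts below 5% and "Absence of peripheral leukemic blasts, EMD" negative. No transfusion entry appears.
- CR without MRD has the CR counts and a marker condition, also with no visible transfusion entry.
- MLFS needs marrow clearance only; counts are not applicable.
- The table's transfusion footnote belongs to another category: "Transfusion independence for hematologic response is defined as the absence of any red blood cell or platelet transfusion during any consecutive" period.

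**Endpoints, Section 6.4.** For AML, the plan has "complete remission rate (CRR) defined as CR + CRi + CRh". MLFS counts in ORR but not in CRR. For MDS, CRR is CR alone, and ORR is CR, CRh, marrow CR and PR. CRR and ORR are the efficacy variables of focus.

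**Use of the qualifier elsewhere.** The AML progression definition in Section 6.4 refers to improvement in ANC "and/or platelet count > 50 x 10 9 /L non-transfused".

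**MDS, Appendix E, Table 21.** The CR row sets hemoglobin of at least 11 g/dL, platelets of at least 100 and neutrophils of at least 1.0 x 10^9/L, with no transfusion condition. The row "Morphologic CR with partial hematologic recovery (CRh") is similar with lower platelet and neutrophil limits. The header requires responses to last at least 4 weeks; a footnote allows earlier classification if further treatment starts sooner.

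**Transfusions on study.** Section 7.2.1.2 allows supportive care "including antibiotics and transfusions" at the investigator's discretion.

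**The concern.** CRh is the only component of AML CRR that neither states nor inherits a transfusion entry. A platelet count can be lifted over 50,000 by a transfusion given shortly before the blood draw, and no duration requirement for AML CRh is visible in Table 19. Followed literally, the table can turn a subject with a clear marrow but no platelet recovery of their own into a remission.

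The boundary matters because it is where CRR and ORR part: MLFS is outside CRR and CRh is inside. The Safety Review Committee also looks at preliminary efficacy when choosing expansion doses and at emerging response data when recommending continuation. Two sites could score the same patient differently, one applying a transfusion-free convention and the other applying the table as printed.

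**Working it through.** The plan gives no figure to reproduce here; the check is on the definitions, followed by an illustration of size.

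**Step 1. Classify example AML subjects.** All have marrow blasts below 5%, no peripheral blasts and no extramedullary disease. Assumptions: the CR transfusion entry means transfusion-free, CRi inherits it, and the *or* in CRi allows one cytopenia only.

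| ANC | Measured platelets | Recent platelet transfusion | Table 19 as written | With a transfusion condition on CRh |
|---|---|---|---|---|
| 1,200 | 60,000 | yes | CRh (in CRR) | MLFS (not in CRR) |
| 700 | 60,000 | yes | CRh (in CRR) | MLFS (not in CRR) |
| 1,200 | 120,000 | yes | CRh (in CRR) | MLFS (not in CRR) |
| 1,200 | 40,000 | yes | MLFS | MLFS |
| 700 | 60,000 | no | CRh | CRh |

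The first three rows change. ORR does not, because it already contains MLFS.

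**Step 2. How far this depends on the damaged cell.** Suppose the CR entry is not a transfusion-free condition. The subject at 1,200 and 60,000 is then CRi anyway, and the subject at 1,200 and 120,000 is CR, so both are in CRR whatever CRh says. The subject at 700 and 60,000 has both counts low and remains MLFS without CRh, provided CRi allows only one cytopenia. That profile is the least dependent on the missing operator.

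**Step 3. Subjects who are in CRR regardless.** Without a recent transfusion, ANC of at least 1,000 with platelets of, say, 35,000 meets CRi, which has no platelet floor. Since the summary uses best overall response, one transfusion-free assessment meeting CRi puts the subject in CRR. Only subjects who never have such an assessment are affected.

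**Step 4. Size.** Each reclassified subject moves CRR by 1/n. Cohort sizes are redacted, so n is assumed: 1/20 = 5.0 points, 1/30 = 3.3, 1/40 = 2.5.

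The 90% limits are the plan's exact Clopper-Pearson type: lower = Beta quantile at 0.05 with parameters (x, n - x + 1); upper = Beta quantile at 0.95 with (x + 1, n - x). For illustration, start from 15%, which the Introduction gives as the ceiling for CRR in most relapsed or refractory AML with unfavorable features, and suppose two such subjects:
- n = 20: 3/20 = 15% (4.2 to 34.4) becomes 5/20 = 25% (10.4 to 45.6).
- n = 40: 6/40 = 15% (6.7 to 27.5) becomes 8/40 = 20% (10.4 to 33.2).

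The two subjects are hypothetical; the documents give no frequency.

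**Step 5. MDS.** Because MDS CRR is CR alone, only the CR row can change it. The CRh and PR rows can affect only ORR, and moving a subject from marrow CR to CRh does not change even that. The 4-week rule should stop a single transfused count from qualifying, but repeated transfusion or the early-treatment footnote could still let one through.

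**The case against.** The strongest reply is that the finding rests on a cell whose operator is lost, and that many affected subjects would reach CRR through CRi. Both points stand and limit the size, as Steps 2 and 3 show. Neither supplies a transfusion condition for CRh. It is also fair that efficacy is secondary and preliminary, that analyses are descriptive and non-comparative, and that investigators may apply a transfusion-free convention unprompted.

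A reader might infer several stronger things that the documents do not support:
- *That CRR is inflated.* It can be; nothing shows how often transfused CRh would occur.
- *That the MLFS route applies to MDS.* Table 21 has no MLFS category, and MDS CRh and PR are outside MDS CRR.
- *That growth factors are a gap specific to CRh.* No response row mentions them, the visible text speaks only of prior use, and the concomitant-medication section is partly redacted.
- *That red-cell transfusion can create an AML response.* The AML CR, CRh and PR rows set no hemoglobin threshold.
- *That the progression definition contradicts CRh.* Its non-transfused clause qualifies a marrow-blast progression criterion, concerns different patients, and can be met through ANC. It shows only that the protocol specifies non-transfused platelets where it wants them.
- *That CRh outranks CRi.* The documents state no such order.

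**Conclusion.** The point holds for AML CRh. As printed, a platelet count above 50,000 that is due only to a recent transfusion can place a marrow-clear subject in AML CRR who would otherwise be MLFS. The effect is 1/n per subject, 2.5 to 5 points for an assumed n of 40 to 20. The total is unknown, and ORR is unaffected. The conclusion rests on reading the CR transfusion entry as transfusion-free or, for subjects with both counts low, on CRi allowing only one cytopenia.

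The MDS CR row has a separate and smaller gap, partly closed by the 4-week rule. This is a correction worth making rather than a fault that undermines the plan, since the endpoint is secondary and descriptive.

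**What to change.** In Table 19, carry the CR row's transfusion condition into the CRh and CR without MRD rows, so that a platelet count taken within a stated window after a platelet transfusion does not qualify. In Table 21, add the same condition for platelets and hemoglobin to the CR row. The sponsor should fix the length of the window before CRR is analysed, because choosing it afterwards would be data-driven. No growth-factor condition is needed for this point, and no red-cell or erythroid condition is needed for the AML counts.

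Report CRR both with and without transfusion-supported responders. Section 6.4 already provides for collecting red-cell and platelet transfusions until End of Treatment or efficacy follow-up, whichever is later, so the flag can be derived without new data collection. The cost is a footnote to each table, one derivation and one extra summary line; reported CRR may be slightly lower.

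### AML progression is dated by a different rule from the one that defines it; and, if duration of response uses the stated events, marrow regrowth counts later after MLFS than after CRi

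*Combined protocol and SAP*

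**What the plan says.** **Definition of AML progression (Section 6.4).** There are three limbs.

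- Marrow: a more than 50% "increase in bone marrow blast count percentage from the baseline (screening) bone marrow blast count", with at least 15 percentage points required when screening is below 30%; "or persistent bone marrow blast count > 70%, over at least 3 months". A count qualifier follows, "without at least a 100% improvement in ANC to an absolute level" and/or a platelet level. The punctuation does not show whether it governs one or both marrow routes.
- Blood: a rise of more than 50% that takes peripheral blasts above 25 x 10^9/L.
- New extramedullary disease.

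**Date of AML progression (same section).** The date is the earliest of three events. For blood, the event is "a doubling of the peripheral blood (PB) blast count". For a rising marrow, it is an increase of more than half over the baseline value. For a marrow that stays high, the sentence reads "a persistence of BM blasts > 70% in subjects with a baseline BM blast count of > 70" (per cent).

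**Relapse (Appendix C, Table 19).** The row label limits hematologic relapse to four states: "Hematologic relapse after CR MRD -, CR, CRi, CRh". The criterion is reappearance of blood blasts, or marrow blasts of 5% or more "not attributable to any other cause (eg, bone marrow regeneration after consolidation therapy) or EMD" positivity. The Stable Disease row is the absence of every response state, ending "CRi, CRh, PR, MLFS; and criteria for PD not met".

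**Endpoints.** Sections 6.4 and 9.6 and Table 3 count MLFS and PR in the AML ORR and list duration of response and PFS. Section 9.6 reports PFS at 6 and 12 months. No readable text gives the event that ends a response. Table 3 tags its efficacy row with footnote a, which is not legible.

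**The concern.** A progression date should follow from the definition of progression. Here the two sentences use different thresholds and cover different limbs. A programmer can therefore meet a subject who has progressed but has no date, or whose date belongs to a marrow that was not yet progression. Any endpoint that uses the progression date inherits this, PFS first.

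The second issue is one of consistency among responders. MLFS and CRi share the same marrow limit (below 5% blasts), and both count in ORR. The stated relapse event exists for one and not for the other. If duration of response is built only from the stated events, one Kaplan-Meier curve would mix two very different thresholds for losing a response.

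**Working it through.** **1. Definition against date**

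Let b be screening marrow blasts in per cent. The plan gives no screening distribution, so the values of b are assumptions.

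- Rise route, definition: max(1.5b, b + 15) if b < 30; otherwise above 1.5b.
- Rise route, date: above 1.5b, with no 15-point minimum.
- Since b + 15 > 1.5b whenever b < 30, the two differ for every b below 30.

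| b | 1.5b | b + 15 | Progression met at | Datable from just over |
|---|---|---|---|---|
| 20 | 30 | 35 | 35 | 30 |
| 25 | 37.5 | 40 | 40 | 37.5 |
| 30 | 45 | not required | just over 45 | 45 |
| 40 | 60 | not required | just over 60 | 60 |

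The persistence route (above 70% for 3 months) is dated only if b > 70.

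- 1.5b exceeds 70 when b > 70/1.5 = 46.7. For b between 46.7 and 70, marrow blasts held above 70% but not above 1.5b meet the definition and have no marrow date. With b = 60, that is any level above 70% and up to 90%.
- The rise route is unreachable when 1.5b ≥ 100, that is b ≥ 66.7. For b from 66.7 to 70, the dating sentence therefore offers no reachable marrow date at all.
- Where the route is dated, the sentence does not say whether the date is the start or the end of the persistence period. The two differ by at least 3 months, half the interval to the 6-month PFS estimate.

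For blood blasts, let B be the starting count in 10^9/L, assumed to be the same reference in both sentences. The definition needs a count above max(1.5B, 25); the date needs 2B. These cross at B = 25/2 = 12.5. Below 12.5, the doubling can come before the limb is met. Above 12.5, the limb is met before the doubling, and a count that stays in between has no date.

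New extramedullary disease does not appear in the dating sentence. Nor does the count qualifier.

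**2. Regrowth after MLFS against regrowth after CRi**

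Take screening 40%, response marrow 3%, later marrow 45%, with no blood blasts and no extramedullary disease.

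- After CRi: 45 ≥ 5, so this is a relapse unless otherwise attributable.
- After MLFS: the relapse row does not apply. 45 < 60 (1.5 x 40) and 45 < 70, so it is not progression either.
- The visit fits the Table 19 Stable Disease row. Section 6.4, however, describes stable disease as never having responded. Neither text says whether the response has ended.

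From the table, for b of 20% to 40%, progression after MLFS is met at about 35% to 60%. That is 35/5 = 7 to 60/5 = 12 times the relapse cut. It is datable from just over 30% (30/5 = 6 times) to 60%. If the count qualifier also governs the rise route, progression could be met later still.

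PR has the same gap: Table 19 has no relapse row for it. The Protocol Summary mentions relapse from PR among reasons for discontinuation, but the readable criteria define that only for MDS (Table 21).

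**The case against.** The strongest objection is to the second part. A reader might infer that the plan never says what ends a response. The documents do not support that: Table 3 footnote a is attached to this very row and was lost, so it may hold the definition. The second part therefore stands only as a conditional. The first part does not depend on the footnote, because both conflicting sentences are legible in Section 6.4.

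A reader might also turn the 6- to 12-fold gap in blasts into a known bias in time. That is not supported. No doubling time is given and the marrow schedule is not legible, so 5% and 60% could fall between the same two marrows. Blood or extramedullary events may come first. Efficacy visits after end of treatment stop at new anticancer therapy (Section 6.3.2), so some subjects may never be observed at the progression level. The direction is plausible; the size is unknown.

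Nor should one read 35% as the lowest level at which regrowth can be dated, since at 20% screening the dating sentence allows just over 30%. For screening between 46.7% and 66.7%, it would also be wrong to say that the 3-month route always governs: a marrow above 1.5b is progression without waiting and may come first.

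On the first part, the dating sentence may be deliberate back-dating to the first sign of progression. That could explain 30% against 35%, and an early doubling. It cannot explain the routes that have no date.

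**Conclusion.** The first part holds on the text alone: Section 6.4 leaves some AML progressions undated and shifts the date of others. How many subjects are affected depends on their screening blasts and on which limb they meet, neither of which is given.

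The second part holds if duration of response uses the stated relapse and progression events. The gap in blast level is then large, but it concerns only responders whose best response is MLFS (or PR, which needs its own event) and whose regrowth is confined to the marrow; that share is not stated. CRR excludes MLFS and PR and is unaffected, and all analyses are descriptive. The priority is low to moderate.

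**What to change.** **Section 6.4, progression date.** Leave the definition as it is and rewrite the dating sentence so that the date is the first assessment at which any limb of the definition is met, including new extramedullary disease. State the date convention for the 3-month persistence route and the scope of the count qualifier.

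**Sections 6.4 and 9.6, duration of response, for analysis only.** Unless footnote a already does so, apply the full Table 19 hematologic relapse criterion after MLFS as after CRi, keeping the exclusion of blasts explained by another cause. State one loss-of-response event for PR, chosen by the sponsor. No treatment-stopping rule is proposed.

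**Cost.** A few sentences and one derivation, on marrow and blood data already collected. Attribution of blasts after MLFS or PR needs the investigator's assessment, which the plan names only for relapse after CR, CRi or CRh. Event-triggered marrows are named only for confirming CR, CRi or CRh, for relapse after those states and for progression, so loss of MLFS or PR would be dated mostly from scheduled marrows. Reported durations may become slightly shorter.
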